## **6.9. Non-Protocol Anticancer Therapy (NPACT)**

For the purpose of supporting safety evaluations:

Concomitant and subsequent (see definition in [Section 4.6](#)) non-radiation NPACT will be summarized by ATC text and WHO Drug base substance preferred name in the Safety population.

For the purpose of supporting efficacy evaluations:

Concomitant and subsequent NPACT will be summarized by treatment group in the PITT and ITT population as follows:

- NPACTS will be summarized by ATC text and WHO Drug based substance preferred name by the following categories: systemic, local, other, and unknown
- Time to first systemic NPACT from randomization date will be summarized by descriptive statistics

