## 4. GENERAL CONVENTIONS

The statistical principles applied in the design and planned analyses of this study are consistent with International Conference on Harmonization (ICH) E9 and E9(R1) guidelines (ICH 1998 and 2019) and FDA guidance's for Industry on Multiple Endpoints in Clinical Trials (2017) and for handling Clinical Trial Endpoints for Approval of Cancer Drugs and Biologics (2018).

Continuous data will be summarized using descriptive statistics (number of observations, mean, standard deviation, median, 25th and 75th percentiles, minimum, and maximum). Frequencies and percentages will be used for summarizing categorical (discrete) data.

Confidence intervals (CIs), when presented, will generally be constructed at the 95% level. For binomial variables, the Clopper-Pearson method (Clopper and Pearson 1934) will be employed unless otherwise specified.

A month is operationally defined to be 30.4375 days. Six months is operationally defined to be 183 days.

Efficacy summaries will be presented by treatment arm randomized to and safety summaries by treatment received unless otherwise specified.

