#### **4.4. Missing and Partial Data**

In general, other than for partial dates, missing data will not be imputed and will be treated as missing. The algorithms for imputation of partial dates vary depending upon the parameter.

Data imputation rules are presented in [Appendix A](#).

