### 7.1.7. Alternative Estimands

Four alternative estimands for PFS arising from changes in strategy for handling some intercurrent events are as defined below:

- Alternative estimand 1 changes the strategy for selected clinical intercurrent events to “composite,” resulting in an endpoint that includes as events earlier of either radiographic progression per BIRC, clinical deterioration, receipt of systemic non-protocol anti-cancer medications, receipt of radiation therapy to soft tissue for disease under consideration or surgical resection of target tumor lesions or death.

- Alternative estimand 2 changes the strategy to “composite” only for systemic non-protocol anti-cancer medications, yielding an endpoint that includes as events earlier of either radiographic progression (as well as death) or initiation of systemic NPACT.
- Alternative estimand 3 changes the strategy to “composite” for systemic non-protocol anti-cancer medications and missed tumor assessment yielding an endpoint that includes radiographic progression as well as death despite missed tumor assessments or initiation of systemic NPACT.
- Alternative estimand 4 changes the strategy to “composite” only for missed tumor assessment yielding an endpoint that includes radiographic progression as well as death despite missed tumor assessments.

More details are provided in [Table 10](#).

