### 7.5.1. Objective Response Rate (ORR) by BIRC

For each subject, best overall response (BOR) is defined as the best tumor assessment category as determined per RECIST 1.1 by BIRC that occurs through the first overall time point response of PD and prior to any of the censoring events defined for the primary analysis of PFS as described in [Section 7.1](#). Tumor assessment categories are ranked as: confirmed CR, PR, SD, progressive disease (PD) and not evaluable (NE). To be classified as confirmed CR or confirmed PR, confirmation must have occurred on a subsequent visit that is  $\geq 28$  days after the response was first observed. To be classified as SD, at least one overall time point response of SD must be documented  $\geq 56$  days after randomization. The ORR is defined as the proportion of subjects with a best response (BOR) of confirmed CR or confirmed PR.

Descriptive testing for ORR will be performed using an unstratified two-sided chi-squared test at 5% level of significance. If a sufficient number of responders are observed, analysis using the

Cochran-Mantel-Haenszel method to adjust for the stratification factors (see [Section 2.5](#)) will be generated.

Point estimates of ORR for each study treatment arm, the difference in ORR between the study treatment arms, and associated  $(1-\alpha)$  % confidence intervals will be provided. The odds ratio and associated  $(1-\alpha)$  % confidence intervals will also be presented. The 2-sided CIs for the point estimate of ORR will be calculated using the Clopper Pearson's method. The 2-sided CIs for the difference in ORR between the two study treatment arms and for the odds ratio will be calculated using asymptotic methods. All summaries for ORR will be provided for the ITT and PITT populations.

Time to objective response is an arithmetic summary amongst those with an objective response and is defined as time from randomization to the first CR or PR that is subsequently confirmed. Time to objective response will be summarized with descriptive statistics.

Waterfall plots displaying maximum percent tumor reduction since baseline in target lesions will be generated for tumor assessment data per BIRC.

These plots will include subjects with a tumor assessment at baseline and at least one post-baseline visit. For each subject, data on or after the progression/censoring date of the respective PFS analyses described in [Section 7.1](#) will be excluded from the waterfall plots.

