### **7.5.3. Duration of Objective Response (DOR)**

Duration of objective response (DOR) is defined as the time from the first documentation of objective response that is subsequently confirmed at a visit that is  $\geq 28$  days later to disease progression or death due to any cause.

$$\text{Duration of response (months)} = (\text{earliest date of PD or death due to any cause or censoring} - \text{date of first objective response} + 1)/30.4375$$

The DOR will be computed only among subjects who experience an objective response (confirmed CR or confirmed PR). The DOR will be analyzed and presented separately per BIRC and per Investigator for subjects in the ITT and PITT populations. The dates of progression and

censoring for DOR are shown in [Table 8](#) (see column PFS-EP-1 per BIRC and column PFS-EP-3 per Investigator).

The DOR will be analyzed using the same analysis method (Kaplan-Meier) as for the analysis on PFS (see [Section 7.1.5](#)).

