## Appendix G: Time to Onset (TTO) Algorithm

1. Analysis unit: episode
2. Analysis method: KM
3. Analysis population: subgroup of those with the specified PT in a Grouped AE term
4. For time to onset for Grouped AEs of any grade
  - a. For each subject identify all records with PTs that are members of the Group
  - b. Sort records by subject, Group and AE start date
  - c. For each subject select the first PT within each grouping
  - d.  $Aval = (AE\ start\ date - treatment\ start\ date + 1) / 30.4375$
  - e. Consider this as an event (CNSR=0)
  - f. Subjects who do not have any events for a grouping are considered censored and their  $Aval = (\text{end of observation period date} - treatment\ start\ date + 1) / 30.4375$
5. For time to onset of Grouped AEs of grade 3-5 follows above steps (a) to (f) except (a) is modified to include only AEs of grade 3 to 5

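### Time to first systemic non-protocol anticancer therapy is planned as a plain descriptive summary with no censoring or death rule, which compresses any difference between arms around the primary PFS analysis (minor, free to fix)

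*SAP*

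**What the plan says.** SAP 6.9 has a part for supporting efficacy evaluations. It opens: "Concomitant and subsequent NPACT will be summarized by treatment group in the PITT and ITT population as follows". Two bullets follow. The first tabulates the therapies by class, substance and category. The second reads: "Time to first systemic NPACT from randomization date will be summarized by descriptive statistics".

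Two general conventions decide what the second bullet produces. SAP 4 says: "Continuous data will be summarized using descriptive statistics (number of observations, mean, standard deviation, median", with quartiles and range completing the list. SAP 4.4 says: "In general, other than for partial dates, missing data will not be imputed and will be treated as missing". SAP 6.9 names no analysis set for subjects without NPACT, no censoring date and no treatment of death.

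Elsewhere the SAP is more explicit about times to an event:

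- Time to response (7.5.1) is openly restricted: "Time to objective response is an arithmetic summary amongst those with an objective response".
- Duration of response (7.5.3) is not left to descriptive statistics: "The DOR will be analyzed using the same analysis method (Kaplan-Meier) as for the analysis on PFS".
- Time to onset of adverse events of special interest is called descriptive in 8.4, but Appendix G specifies "Analysis method: KM" with a censoring step.

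NPACT timing has neither a restriction label nor an algorithm.

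**The concern.** A subject who has not started NPACT by cutoff has no date and so no value. A plain mean or median then covers only those who started, and their times are cut short by the length of follow-up and by death. In both arms the observed times crowd into the same window. An arm with fewer and later starts can therefore show almost the same average as the other arm. If a small group in one arm starts early, that arm can look worse although far fewer of its subjects ever start.

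The quantity bears on two questions that the documents raise themselves. Systemic NPACT is one of the reasons for censoring in the primary PFS analysis (SAP Table 8). Protocol 1.7.2 warns that subsequent treatment could confound the effect on OS. How soon each arm moves to other systemic therapy is useful context for both, and this output is the only one planned to show that timing on its own.

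**Working it through.** **Check of borrowed design inputs.** The documents state no figure for time to NPACT, so there is none to reproduce. The design values used below are self-consistent: 11.6 / 0.66 = 17.6 months (PFS), 48 / 0.73 = 65.8 months (OS), and the largest significant PFS hazard ratio is exp(−2 × 1.96 / √249) = 0.780, matching the stated 0.78.

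**Inputs**

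- Death medians: 48 and 65.8 months (SAP 2.4).
- Accrual: 40 per month (SAP 2.4), so 550 subjects take 550 / 40 = 13.75 months.
- Minimum follow-up of the first 550: 15.6 months (SAP 4.8.1). Follow-up is then taken as uniform from 15.6 to 15.6 + 13.75 = 29.35 months.
- NPACT medians: assumed, over a range.

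**Formula.** Let λ = ln 2 / (NPACT median) and μ = ln 2 / (death median). Among subjects who start NPACT before death and cutoff, the density of the start time is proportional to λ exp(−(λ + μ)t) × Pr(follow-up > t). The recipient mean is the mean of that density. The proportion with NPACT is its integral before scaling.

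**Recipient means at PITT follow-up (control vs experimental)**

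| Assumed NPACT medians (months) | Proportion with NPACT | Recipient mean (months) | Apparent increase |
|---|---|---|---|
| 15 vs 22.7 | 56% vs 44% | 8.8 vs 9.6 | about 10% |
| 18 vs 27.3 | 50% vs 39% | 9.1 vs 9.9 | about 8% |
| 18 vs 36 | 50% vs 31% | 9.1 vs 10.15 | about 11% |
| 24 vs 36.4 | 41% vs 31% | 9.5 vs 10.2 | about 6% to 7% |

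The true increase in median is about 50% in three rows and 100% in the third.

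**Possible reversal.** Keep a control median of 18 months. In the experimental arm let 15% start early (median 4 months) and the rest late (median 60 months). NPACT use is then 31% against 50% in control, yet the recipient mean is 8.1 against 9.1 months. The arm with much less NPACT appears to start it sooner.

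**Dependence on the data cut.** Here the PFS medians stand in for NPACT timing as the base case (11.6 months, hazard ratio 0.66), so the true difference is 11.6 / 0.66 − 11.6 = 6.0 months.

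| Cut | Recipient medians (months) | Difference shown | Share of 6.0 months |
|---|---|---|---|
| 440 subjects, 23 months | 6.0 vs 6.8 | 0.8 | 14% |
| 550 subjects, minimum follow-up 15.6 months | 6.9 vs 8.1 | 1.2 | about 20% |
| 840 subjects, 23 months | 4.6 vs 5.2 | 0.6 | 10% |
| 840 subjects, 69 months (final OS) | 9.2 vs 12.8 | 3.6 | 60% |

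For control medians from 11.6 to 24 months, with and without competing death, the share shown is 2% to 21% around the primary analysis and 27% to 68% at 69 months.

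**What a method that handles death and censoring shows.** With NPACT or death as the event, the base-case medians are 1 / (1/11.6 + 1/48) = 9.3 and 1 / (1/17.6 + 1/65.8) = 13.9 months, a visible difference of about 4.5 months. Cumulative incidence of NPACT at time t with death competing is λ/(λ + μ) × (1 − exp(−(λ + μ)t)). For NPACT medians of 18 vs 27.3 months at 12 months:

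- Control: 48/66 × (1 − exp(−0.0530 × 12)) = 0.727 × 0.470 = 34%.
- Experimental: 65.8/93.1 × (1 − exp(−0.0359 × 12)) = 0.707 × 0.350 = 25%.

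Recipient means in the same scenario are 9.1 and 9.9 months.

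**The case against.** The strongest reply is that little depends on this line. Time to NPACT is not a listed endpoint, carries no test, and sits under treatments and medications. The OS estimand is treatment policy, so NPACT timing is context for OS and not a correction to it. That stands, and it is why the point is minor.

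Second, much of the information appears elsewhere. SAP 6.9 tabulates NPACT use by arm, so a gap such as 50% against 39% would be seen. PFS-EP-12 turns NPACT-censored subjects into events at first NPACT in both arms, and PFS-EP-14 does so in the experimental arm only. PFS-EA1 to EA3 also count NPACT as an event. SAP 7.1.7 describes EA2 as "yielding an endpoint that includes as events earlier of either radiographic progression (as well as death) or initiation of systemic NPACT". These analyses address bias in PFS more directly than an NPACT curve would. This stands in part: percentages carry no timing, and the composite analyses mix NPACT with progression and death.

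Third, the restriction to recipients is an inference. SAP 8.4 shows that the SAP can say descriptive and mean Kaplan-Meier. The ambiguity is real, but Appendix G resolves it for adverse events and nothing resolves it for NPACT. A programmer following SAP 4 and 4.4 would produce the recipient-only table.

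A reader might also infer that NPACT is the main reason for censoring in the primary PFS analysis. The documents do not support that. Table 8 lists censoring rules without counts, and ongoing observation, missed assessments, target-lesion surgery and soft-tissue radiation also censor.

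**Conclusion.** The point holds as a minor one. As written, SAP 6.9 most naturally yields a recipient-only mean and median for a time-to-event quantity, with no rule for censoring or death. Around the primary PFS analysis that output would show a true 1.5- to 2-fold difference in median as about 6% to 11% in means, and it can reverse the apparent order of the arms.

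It is tempting to conclude that the summary hides most of any difference at every analysis. The calculations do not support that: the statement is limited to the primary PFS cut, since about 60% of the difference in medians shows at 69 months in the base case.

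The sizes rest on assumed exponential NPACT times, independent exponential death at the design medians, and constant accrual. The direction of the compression follows from limited follow-up; its size depends on the true rates. No primary or secondary result, alpha, power or sample size is affected.

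**What to change.** Replace the line in SAP 6.9 with the cumulative incidence of first systemic NPACT from randomization, by arm, in the PITT and ITT populations. Treat death without NPACT as a competing event, and censor subjects alive without NPACT at last contact. Report the curves, numbers at risk, and estimates at 6, 12, 18 and 24 months.

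If Kaplan-Meier is preferred, make the event NPACT or death. Censoring at death would overstate the incidence of NPACT. If the recipient-only table is kept, label it as restricted to subjects who started NPACT before cutoff.

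The cost is one SAP line and one standard output. NPACT and survival status are already collected (Protocol 5.4 and 5.7.12), partial NPACT start dates already have an imputation rule (SAP Appendix A), and SAP 4.8 provides for documenting such a change before the analysis is run. The 24-month estimate will rest on fewer subjects at the primary cut, which the numbers at risk will show.

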## **6.10. Concomitant and Subsequent Surgeries/Procedures/Radiations/Transfusions**

Concomitant and subsequent surgery/procedures that impacted the target lesion(s) (Yes, No, Unknown) will be summarized by treatment group in the ITT, PITT, and Safety populations.

Frequency counts and percentages will be presented for concomitant and subsequent radiation therapy indication, type and site by treatment group in the ITT, PITT, and Safety populations.

Concomitant transfusions will be summarized by transfusion type and treatment group for subjects in the Safety population.

## 7. EFFICACY ANALYSES

Efficacy summary details for primary, secondary and additional endpoints are described in the below sections.

### 7.1. Primary Efficacy Endpoint (PFS)

The primary efficacy endpoint is duration of PFS as determined by the BIRC per RECIST 1.1.

#### 7.1.1. Primary Estimand

The primary estimand for PFS is the difference in survival functions between treatment conditions in the duration of radiographic PFS in the targeted population:

- irrespective of whether the assigned study treatment was given
- irrespective of clinical deterioration
- irrespective of whether local radiation was given to bone
- irrespective of surgical resection of non-target lesions
- had systemic non-radiation NPACT not been given
- had surgery to resect target tumor lesions not occurred
- had local radiation to soft tissue not been given
- had not missed 2 or more adequate tumor assessments

Estimands are derived as follows:

**Table 7: Estimand Definition and Rationale for Primary Estimand**

Estimand Attribute 	Primary Definition		Rationale (as needed)
Population	Subjects randomized into the study intended to include subjects with untreated advanced or metastatic RCC of intermediate or poor risk per IMDC ( Section 2.1 )		The initial clause “Subjects randomized into the study intended to include...” is included to align the estimand with the application of the ITT principle expected by regulatory reviewers.
Endpoint	Duration of radiographic PFS		
Intercurrent events	Event	Strategy	Rationale (as needed)
	Receipt of non-assigned study treatment	Treatment policy	This strategy applied to align the estimand with the application of the ITT principle expected by regulatory reviewers.

Estimand Attribute 	Primary Definition		Rationale (as needed)
	Clinical deterioration	Treatment policy	This strategy applied due to the nature of the primary endpoint, which is radiographic PFS.
	Receipt of local radiation to bone	Treatment policy	This strategy applied as local radiation to bone is typically palliative and does not directly confound radiographic evaluations of soft tissue.
	Surgical resection of non-target tumor lesions	Treatment policy	This strategy applied as target lesions are the primary focus of RECIST 1.1 evaluations.
	Surgical resection of target tumor lesions	Hypothetical	This strategy arises as a consequence of the convention of censoring for these intercurrent events that confound radiographic tumor assessments per RECIST 1.1., and the assumption in the Kaplan-Meier model that censored subjects would have behaved in a manner similar to those not censored, ie. not experienced these intercurrent event(s)
	Receipt of systemic non-protocol anti-cancer medications	Hypothetical	
	Receipt of local radiation to soft tissue for disease under study	Hypothetical	
	Missed 2 or more adequate tumor assessments	Hypothetical	
Population summary	Difference in survival functions between treatment conditions as assessed by stratified log-rank test and characterized by the hazard ratio.		

See [Appendix E](#) for estimand terminology

### 7.1.2. Definition of PFS

For the primary analysis used to characterize the primary estimand, duration of PFS is defined as the time from randomization to the earlier of either the date of radiographic progression per BIRC or the date of death due to any cause:

$$\text{PFS (months)} = (\text{earliest date of progression, death, censoring} - \text{date of randomization} + 1) / 30.4375$$

### 7.1.3. Hypothesis

The hypotheses to be evaluated in the analysis of the PFS are:

$$H_0: S(t)_{\text{cabozantinib+nivolumab+ipilimumab}} = S(t)_{\text{placebo+nivolumab+ipilimumab}}$$

$$H_A: S(t)_{\text{cabozantinib+nivolumab+ipilimumab}} \neq S(t)_{\text{placebo+nivolumab+ipilimumab}}$$

where  $S(t)_{\text{cabozantinib+nivolumab+ipilimumab}}$  and  $S(t)_{\text{placebo+nivolumab+ipilimumab}}$  are the survivor functions for PFS for the experimental and control arms, respectively.

#### 7.1.4. Conventions for Analysis

Only adequate tumor assessments (ATAs) will be considered in the determination of radiographic progression and censoring dates. For the purpose of this study, an ATA is defined as one that results in a time point assignment of complete response (CR), partial response (PR), stable disease (SD; non-CR, non-PD), or progression, or not applicable (NA). Note that NA is assigned when a subject does not have any evidence of measurable or non-measurable disease.

The recorded date of radiographic progression is the date of the tumor assessment visit at which progression is declared. If multiple scan dates are associated with a tumor assessment visit, the earliest scan date within the set will be chosen as the progression date.

General censoring rules for the primary analysis of PFS are provided in [Table 9](#) (analysis ID PFS-EP-1).

#### 7.1.5. Primary Analysis

The timing of this analysis is event-driven and will be conducted after at least 249 events have been observed in the PITT population (the first 550 randomized subjects; see [Section 4.8.1](#)). It is designed to include progression events as determined by the BIRC per RECIST 1.1 or death whichever occurs earlier. Clinical deterioration determined by the Investigator will not be considered as progression events. If more than 249 events are included in the data cut off for the first 550 subjects, the primary analysis of PFS will include the first 249 events; supportive analysis including all PFS events in this population will also be provided. An additional supportive analysis of all PFS events in the first 440 randomized subjects through the data cutoff will be performed.

The hypothesis testing between experimental arm compared to the control arm will be performed using the stratified log-rank test with  $\alpha=0.05$  level of significance. The stratification factors are as described in [Section 2.5](#), and the values used for analysis will be those recorded in the IxRS.

The median duration of PFS along with the associated 95% CI for each study treatment arm will be estimated using the Kaplan-Meier method. The stratified HR and its 95% CI will be estimated using a Cox proportional-hazard model with treatment group as the independent variable using the same stratification factors as were used for the log-rank test.

If the p-value for the stratified log-rank test is less than the critical value for rejecting the null hypothesis and the HR ( $\lambda_{\text{cabozantinib} + \text{nivolumab} + \text{ipilimumab}} / \lambda_{\text{placebo} + \text{nivolumab} + \text{ipilimumab}}$ ) is  $< 1$ , the null hypothesis of no difference between the two study treatment arms will be rejected and it will be inferred that duration of PFS is greater in the experimental arm compared to the control arm.

The unstratified versions of all the above analyses will also be conducted.

A summary of concordance between the IRC and Investigator determinations of radiographic progressive disease per RECIST 1.1 (rPD) status, and rPD dates will also be provided.

